2.15.5.3 Handling of missing values/censoring/discontinuations

The additional analysis will be performed only for the observed data at Week 104 , hence missing data will not be imputed.

[Redacted]

[Redacted]

[REDACTED]

2.15.9 Investigators global assessment mod 2011 score and response over time

Treatment Arm A1 will be compared with Arm B1 based on IGA mod 2011 0/1 responses at Week 104 using a similar logistic regression model as described in [Section 2.7.1](#). Analysis will be performed on FUP efficacy analysis set on observed data only.

IGA mod 2011 score will be summarized descriptively, using number and percentages by visits. Confidence intervals for response rates will be derived as well based on the score method including continuity correction ([Newcombe 1998](#)). Graphical presentation will be performed for responders (%) at each scheduled visit from observed data using scatter plot.

IGA mod 2011 score will be summarized descriptively, using number and percentages by visits. Confidence intervals for response rates will be derived as well based on the score method including continuity correction ([Newcombe 1998](#)).

[REDACTED]

3 Sample size calculation

The sample size calculation is performed for the primary endpoint (proportion of PASI 90 responders at Week 52) and the key secondary endpoint (proportion of all randomized subjects who achieve PASI 90 response at Week 104). The selected total sample size is 160 subjects, such that 80 subjects are randomized in each arm.

The sample size calculation based on the proportion of PASI 90 responders at Week 104 was performed using PASS 11.

The power calculations for the primary endpoint are based on the asymptotic Wald test to compare secukinumab 300 mg s.c. versus nb-UVB using the hierarchical method to adjust for multiplicity. Based on data (unpublished) and experiences from recent studies, it is assumed that the proportion of PASI 90 responders at Week 52 will be around 70% after early treatment with secukinumab 300 mg s.c. (Arm A1) and around 35% after 1 or 2 cycles of nb-UVB treatment (Arm B1). With assumed approximate 0% dropout rate in Arm A1, and 20% in Arm B1 until Week 52 due to lack of efficacy or AEs (considered non-responders), the response rate would change to 70% and 28%, respectively. Assuming an absolute difference of 42% in the proportion of subjects achieving PASI 90 at Week 52, the sample size of 80 subjects in each arm would provide 99.9% power at the 1-sided significance level of 0.025 using asymptotic Wald test for equality of proportions (using PASS 11).

For the Mechanistic Sub-study, additional 12 randomized subjects will be treated for 104 weeks with secukinumab 300 mg s.c. (Arm A2), along with 12 subjects each from Arm A1b and Arm B1b, and will serve as active groups. Further, 12 subjects identified with chronic plaque psoriasis will be allocated to secukinumab 300 mg s.c. for 52 weeks (Arm C1) and another 12 subjects with chronic plaque psoriasis will be treated during 104 weeks with secukinumab 300 mg s.c. (Arm C2), both serving as control groups for the Mechanistic Sub-study. As the Mechanistic Sub-study will not involve any formal testing of hypothesis, the sample size for it is obtained in an illustrative manner.

4 Change to protocol specified analyses

In Study design section , under follow up subsection “PASI90 score” is mentioned in the protocol however it is updated as “PASI90 response”.

Randomized set is added.

[REDACTED]

PASI 75 is added in the section [2.13.2.1](#) and [2.14](#).

[REDACTED]

A new population called Modified full analysis set (mFAS) is introduced. Randomized subjects who received treatment are considered in this population. Primary, key secondary and additional secondary endpoints will be analysed using mFAS along with FAS. [REDACTED]

[REDACTED]

Statistical analysis for Week 156 will be performed at the actual scheduled visit Week 152.

5 Appendix

5.1 Crude incidence and related risk estimates

5.1.1 Crude incidence and 100*(1-α)% confidence interval

For n subjects, each at risk to experience a certain event with probability π , the crude incidence is estimated as $p=x/n$, where x is the number of subjects with the event.

Absolute and relative frequencies will be displayed as well as 95% confidence interval for the relative frequency based on the score method including continuity correction (Newcombe 1998).

With z as $(1-\alpha/2)$ -quantile of the standard normal distribution (SAS: $z=PROBIT(1-\alpha/2)$), n as total number of subjects (i.e. number of subjects in the denominator), and p as estimated crude incidence (number of subjects with event / n) it is $q = 1 - p$.

Then the lower limit is

$$L = \max \left(0, \frac{2np + z^2 - 1 - z \sqrt{z^2 - 2 - \frac{1}{n} + 4p(nq + 1)}}{2(n + z^2)} \right)$$

and the upper limit is

$$U = \min \left(1, \frac{2np + z^2 + 1 + z \sqrt{z^2 + 2 - \frac{1}{n} + 4p(nq - 1)}}{2(n + z^2)} \right)$$

In addition, if $L > p$ then $L = p$ and if $U < p$ then $U = p$.

If appropriate, an exact 100*(1-α)% confidence interval (Clopper-Pearson 1934) will be obtained by using the SAS procedure PROC FREQ with the EXACT BINOMIAL statement. However, the confidence interval derived via the score method including continuity correction will be the default in safety analyses.

5.1.2 Relative risk and 100*(1-α)% confidence interval

For an investigational drug group with n_1 subjects at risk, independent from the control group (nb-UVB) with n_0 subjects at risk, of whom x_1 and x_0 experience a certain event with probability π_1 and π_0 respectively, the relative risk is estimated as p_1/p_0 with $p_1=x_1/n_1$ and $p_0=x_0/n_0$.

An asymptotic 100*(1-α)% confidence interval on the relative risk will be based on the back-transformed large sample confidence limits on the log-transformed relative risk estimate which are obtained by application of the delta-method and Slutsky's theorem (Lachin 2000). The SAS procedure PROC FREQ with option RELRISK in the TABLES statement will be used to provide the asymptotic 100*(1-α)% confidence interval on the relative risk. The estimate is not computed if either x_1 or x_0 equals 0. In this case, or if the crude incidences are low in both groups, the relative risk will be approximated by the odds ratio for which an exact confidence interval will be obtained as specified in Section 5.1.3. If the relative risk is not well

approximated by the odds ratio but asymptotic normality is questionable, STATXACT will be used.

5.1.3 Odds ratio and 100*(1-α)% confidence interval

For an investigational drug group with n_1 subjects at risk, independent from the control group (e.g. placebo or comparator) with n_0 subjects at risk, of whom x_1 and x_0 experience a certain event with probability π_1 and π_0 respectively, the odds ratio is estimated as

$\frac{p_1 / (1 - p_1)}{p_0 / (1 - p_0)}$ with $p_1 = x_1/n_1$ and $p_0 = x_0/n_0$. A conditional exact 100*(1-α)% confidence interval will be obtained by using the SAS procedure PROC FREQ with statement EXACT OR.

5.2 Exposure adjusted incidence rate and related risk estimates

5.2.1 Exposure adjusted incidence rate and 100*(1-α)% confidence interval

It will be assumed that for each of n subjects in a clinical trial the time t_j ($j=1, \dots, n$) to the first occurrence of a certain treatment emergent event is observed, or if the event was not experienced, the (censored) time to the end of the observation period or last dose plus 84 days whichever occur earlier. The sequence of first occurrences of an event will be modeled to follow approximately a Poisson process with constant intensity θ . The rate parameter θ will be estimated as $\lambda = D/T$, where $T = \sum_{j=1}^n t_j$ and D is the number of subjects with at least one event.

Conditionally on T , an exact 100*(1-α)% confidence interval for a Poisson variable with parameter θT and observed value D can be obtained based on (Garwood, 1936), from which an exact 100*(1-α)% confidence interval for D/T will be derived as follows (Sahai, 1993; Ulm, 1990):

Lower confidence limit $L = \frac{0.5c_{\alpha/2, 2D}}{T}$ for $D > 0$, 0 otherwise,

Upper confidence limit $U = \frac{0.5c_{1-\alpha/2, 2D+2}}{T}$

where $c_{\alpha, k}$ is the α th quantile of the Chi-square distribution with k degrees of freedom.

5.2.2 Exposure-adjusted event rate and 100*(1-α)% confidence interval

For each of n subjects t_j ($j=1, \dots, n$) specifies the exposure time. The number of occurrences of a treatment emergent event will be modeled to follow approximately a Poisson process with constant intensity θ . The rate parameter θ will be estimated as $\lambda = D/T$, where $T = \sum_{j=1}^n t_j$ and D is the number of events (episodes). Conditionally on T , an exact 100*(1-α)% confidence interval for a Poisson variable with parameter θT and observed value D can be obtained based on

(Garwood, 1936), from which an exact $100*(1-\alpha)\%$ confidence interval for D/T will be derived as follows (Sahai, 1993; Ulm, 1990):

Lower confidence limit $L = \frac{0.5c_{\alpha/2, 2D}}{T}$ for $D > 0$, 0 otherwise,

Upper confidence limit $U = \frac{0.5c_{1-\alpha/2, 2D+2}}{T}$

where $c_{\alpha, k}$ is the α th quantile of the Chi-square distribution with k degrees of freedom.

5.3 Imputation rules

5.3.1 Study drug

Any partial dates will be imputed as follows:

We take the earlier day of

- The last day in the month and
- The end day of the corresponding phase

5.3.2 AE date imputation

Impute AE end date:

1. If the AE end date 'month' is missing, the imputed end date should be set to the earliest of the (min (last visit date, last dose date + 84 days), 31DECYYYY, date of death).
2. If the AE end date 'day' is missing, the imputed end date should be set to the earliest of the (min (last visit date, last dose date + 84 days), last day of the month, date of death).
3. If AE 'year' is missing or AE is ongoing, the end date will not be imputed.

Impute AE start date:

Before imputing AE start date, find the AE start reference date as below

- If the (imputed) AE end date is complete and the (imputed) AE end date < treatment start date then AE start reference date = min(informed consent date, earliest visit date).
- Else AE start reference date = treatment start date

1. If the AE start date 'year' value is missing, the date uncertainty is too high to impute a rational date. Therefore, if the AE year value is missing, the imputed AE start date is set to NULL.

2. If the AE start date 'year' value is less than the treatment start date year value, the AE started before treatment. Therefore:

a. If AE 'month' is missing, the imputed AE start date is set to the mid-year point (01JulYYYY).

b. Else if AE 'month' is not missing, the imputed AE start date is set to the mid-month point (15MONYYYY).

3. If the AE start date year value is greater than the treatment start date year value, the AE started after treatment. Therefore:

a. If the AE month is missing, the imputed AE start date is set to the year start point (01JanYYYY).

b. Else if the AE month is not missing, the imputed AE start date is set to the later of (month start point (01MONYYYY), AE start reference date + 1 day).

4. If the AE start date year value is equal to the treatment start date year value:

a. And the AE month is missing the imputed AE start date is set to the AE reference start date + 1 day.

b. Else if the AE month is less than the treatment start month, the imputed AE start date is set to the mid-month point (15MONYYYY).

c. Else if the AE month is equal to the treatment start date month or greater than the treatment start date month, the imputed AE start date is set to the later of (month start point (01MONYYYY), AE start reference date + 1 day).

If complete (imputed) AE end date is available and the imputed AE start date is greater than the (imputed) AE end date, then imputed AE start date should be set to the (imputed) AE end date.

Imputed Date Flag

If year of the imputed date is not equal to YYYY then date flag = Y

Else if month of the imputed date is not equal to MON then date flag = M

Else if day of the imputed date is not equal to day of original date then date_flag = D Else date flag = null

Imputed Time Flag

If hours of the imputed time is not equal to hours of original time then time flag = H

Else if minutes of the imputed time is not equal to minutes of original time then time flag = M

Else time flag = null.

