2.8 Safety analyses

All safety evaluations will be performed on the SAF

In general, the following guidelines are proposed for safety analysis:

- Adverse events: Only treatment emergent records are reported in the tables, and listings have the “treatment emergent” flag displayed.
- Other safety data (e.g. laboratory data, vital sign, ECG, Physical examination etc):
 - by visit summary statistics tables: only include “on-treatment” records in the tables, i.e., assessments within last dose plus 84 days cutoff. Listings have the “on-treatment” flag displayed. Follow up visits (eCRF visits) may be summarized separately if required.

For the Main Study, the safety of secukinumab compared with nb-UVB will be evaluated. For the Mechanistic Sub-study, similar safety evaluations will be performed by treatment and study phase.

Entire treatment/study period for Main study (A1a+A1b and B1a+B1b)

Entire treatment period = randomization to Week 52 (EOT); for safety analysis include FU period up to last dose + 84 days.

Entire study period = randomization to end of study (EOS); includes follow up period (Week 208)

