2.8.1 Adverse events (AEs)

For all subjects enrolled in the study, AEs data will be summarized and analyzed together by treatment arms for the SAF.

Treatment emergent AEs are defined as (events started on or after the first dose of study treatment or events present prior to the first dose of study treatment but increased in severity on or after dosing based on preferred term , and within 84 days (inclusive) after the last dose of study treatment. Only primary paths within MedDRA will be considered for AE reporting.

Adverse events will be summarized by presenting, for each treatment arm, the number and percentage of subjects having any AE, having an AE in each primary system organ class and having each individual AE (preferred term).

Summaries will also be presented for AEs by severity (mild/moderate/severe) and for study treatment related AEs. If a particular AE 'severity' is missing, this variable will be listed as missing and treated as missing in summaries.

If a subject reported more than one AE with the same preferred term, the AE with the greatest severity will be presented. If a subject reported more than one AE within the same primary system organ class, the subject will be counted only once with the greatest severity at the system organ class level, where applicable.

The most common adverse events reported ($\geq z$ % in any group for each preferred term in the table by SOC and PT) will be presented in descending frequency according to its incidence in secukinumab group (combining all secukinumab treatment arms) starting from the most common event. Here threshold value z is set to 2 (%) but it may be updated following review of the dry run outputs.

Separate summaries will be provided for psoriatic arthritis, SAEs, other significant AEs leading to discontinuation from the study, and AEs leading to study treatment discontinuation.

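### For a resolved AE with both dates partial, SAP 5.3.2 moves an onset later than last dose + 84 days back onto the last treatment-emergent day, against the recorded month and year

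*SAP*

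**What the plan says.** SAP 5.3.2 imputes the end date first and the start date second.

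- **End date, month missing (rule 1):** the earliest of "min (last visit date, last dose date + 84 days), 31DECYYYY, date of death".
- **End date, day missing (rule 2):** "the imputed end date should be set to the earliest of the (min (last visit date, last dose date + 84 days), last day of the" recorded month and the date of death.
- **Exception (rule 3):** if the year is missing or the "AE is ongoing, the end date will not be imputed".
- **Start date, year after the treatment-start year (rule 3):** the first of the recorded month (or the day after the reference date, if later), or 1 January if the month is missing.
- **Closing rule:** if "the imputed AE start date is greater than the (imputed) AE end date, then imputed AE start date should be set to the" end date.

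SAP 2.8.1 defines a treatment-emergent AE as one that starts or worsens on or after first dose "and within 84 days (inclusive) after the last dose of study treatment". SAP 2.8 adds that "Only treatment emergent records are reported in the tables".

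Under Protocol 7.1, AEs are collected from consent to the end-of-study visit. Protocol 3.1 allows treatment-free observation up to Week 208. AEs that start well after the 84-day window are therefore in the database.

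**The concern.** The last dose + 84 days term belongs to the definition of the on-treatment window. In 5.3.2 it is used to date events, with no condition limiting it to events recorded inside that window. An AE whose recorded month and year lie wholly after the window still receives an end date at the window's close, and the closing rule then drags the imputed start to the same day. That day qualifies as treatment-emergent.

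Off-treatment events would then enter the treatment-emergent incidence tables, the special-interest summaries and the registry-posting tables. In the exposure-adjusted incidence rate (SAP 5.2.1), a subject without an event is censored no later than last dose + 84 days. A first event moved to that day adds one to the numerator and leaves that subject's time at risk unchanged, so the rate rises.

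**Working it through.** **Inputs.** A1 last dose at Week 48 (Protocol 3.1). B1: one or two 12-week cycles with a break of at most 28 weeks (Protocol 3.1). Window: last dose + 84 days, inclusive (SAP 2.8.1). The plan gives no figure to reproduce on this point.

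**Worked example, A1.** Assume first dose on 01JAN2019 and dosing on schedule.

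1. Week 48 is Day 336 + 1 = 337, which is 03DEC2019.
2. The window closes at 03DEC2019 + 84 days = 25FEB2020.
3. The AE is recorded as MAY2021 to JUN2021, days missing, and the patient is still attending visits.
4. End rule 2: the earliest of 25FEB2020 and 30JUN2021 is 25FEB2020.
5. Start rule 3b gives 01MAY2021.
6. 01MAY2021 is later than 25FEB2020, so under the closing rule "then imputed AE start date should be set to the (imputed) AE end date": 25FEB2020.
7. That is day 84 after last dose, so the AE is treatment-emergent, more than 14 months before its recorded month.

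**All post-window onset days.** The rules were applied to each true onset day from last dose + 85 days to just before Week 208. Assumptions: first dose 15JAN2019, AE duration 10 days, last visit at Week 208, and last dose at Week 48 (A1), Week 12 (B1, one cycle) or Week 52 (B1, two cycles). The table gives onset days flagged treatment-emergent.

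| Date pattern | A1 | B1, one cycle | B1, two cycles |
|---|---|---|---|
| Both days missing | 1025/1025 | 1277/1277 | 997/997 |
| Only start day missing | 21/1025 | 29/1277 | 23/997 |
| Start day missing, ongoing | 21/1025 | 29/1277 | 23/997 |
| Only end day missing | 0/1025 | 0/1277 | 0/997 |
| Both complete | 0/1025 | 0/1277 | 0/997 |
| Both days missing, cap at last visit instead | 21/1025 (2.0%) | 29/1277 (2.3%) | 23/997 (2.3%) |

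The counts of 21, 29 and 23 do not come from the cap. They are onsets in the calendar month in which the window closes, where the first-of-month rule alone puts the start inside it.

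With only the end day missing, classification is right, but the imputed end precedes the recorded start on every onset day tested. No AE rule repairs this. The concomitant-medication rules in SAP 5.3.3 do, by moving the end up to the start.

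**Where the window closes, by last dose.**

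- A1: 48 + 12 = Week 60. Protocol maximum exposed: 208 − 60 = 148 weeks.
- B1, one cycle ending at Week 12 (assumption): 12 + 12 = Week 24. Exposed: 208 − 24 = 184 weeks, of which Weeks 24 to 52 (28 weeks) are Treatment Epoch. That leaves 156 weeks of follow-up.
- B1, two cycles at the maximum break: 12 + 28 + 12 = Week 52, so the window closes at Week 64. Exposed: 208 − 64 = 144 weeks.

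**The case against.** **Most follow-up AEs escape.** A reader might infer that any AE starting in the treatment-free period becomes treatment-emergent. The documents do not support that. The cap misclassifies only when both dates are partial with years known, the AE is not ongoing, and onset is after last dose + 84 days. In A1, an onset between Weeks 52 and 60 is treatment-emergent by the SAP's own definition. This objection stands and sets the scope.

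**Arm imbalance.** It is tempting to read the early window closure in single-cycle B1 as a bias against nb-UVB. Two-cycle B1 at the maximum break has a shorter exposed span than A1 (144 against 148 weeks). Patients below PASI 50 at Week 52 and those who relapse leave the study, and the plan expects poorer response in B1, so follow-up time after the window may be greater in A1. The exposed span depends on the last-dose date, but no net direction between arms follows.

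**Few patients remain late.** SAP 2.1 says numbers after Week 104 are low. SAP 2.14.2 reports early termination with 11 patients remaining and a last visit at Week 152. The Week 208 spans are therefore maxima. This stands and limits the count.

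**The change is visible.** The imputed date flag in 5.3.2 marks a changed year or month, and listings carry the treatment-emergent flag. That helps to find affected records but does not correct the tables.

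**Use of the imputed start.** SAP 2.8.1 does not say that treatment-emergent status is derived from the imputed start, as SAP 2.4.2 does for medications. It is nevertheless the natural use of the start-date rules, and no other basis is given.

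**End before start.** The safety sections that can be read specify no AE-duration summary, so this defect affects data consistency and listings rather than a tabulated result.

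**Conclusion.** The rules as written give a wrong result for a defined class of AEs: resolved, both dates partial with known years, onset after last dose + 84 days. For that class the error was certain in the day-missing pattern tested (every onset day, all three last-dose scenarios), and it overrides the recorded month and year. This is not a cautious treatment of ambiguous dates, because the recorded month or year already places the event outside the window, except where it is the month or year in which the window closes.

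The documents do not say how many AEs have both dates partial. Given the attrition and early termination, the count is probably small. No efficacy endpoint is touched. The conclusion assumes that treatment-emergent status uses the imputed start date. The worked dates assume on-schedule dosing, and the Week 24 closure assumes a single cycle ending at Week 12.

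**What to change.** In SAP 5.3.2:

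1. In end-date rules 1 and 2, replace the minimum of last visit and last dose + 84 days with the patient's last contact date (or the data cut-off). Keep the month-end or year-end and death limits.
2. State that no imputed date may fall outside the recorded month and year, and that no imputed end date may precede a complete start date.
3. State that treatment-emergent status is derived after imputation under these rules.

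In the worked example, the AE becomes 01MAY2021 to 30JUN2021 and is not treatment-emergent. About 2% of post-window onset days in the day-missing pattern remain flagged, all in the calendar month in which the window closes. There the recorded date cannot settle the matter, so this is a genuine ambiguity. If the month is also missing, the ambiguous period is the calendar year in which the window closes.

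The cost is a few lines of SAP text, the matching program change and a rerun of the AE outputs. No new data are needed. Where tables already exist, records whose imputed year or month differs from the recorded one can be listed to show how many events move.
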